4.1.3. Dose escalation phase I part procedure for Arm A

The following sections are applicable for the **Arm A** dose escalation phase I part. They will be updated for **Arm B** dose escalation phase I part, according to the results of Arm A.

4.1.3.1. General points

The sponsor will be responsible for the coordination of the clinical trial and will provide regular updates to the centres on the study progress.

The dose escalation phase I part will be conducted in clinical centres which have a proven expertise in phase I studies in oncology. Multicentre study will allow improving patient's recruitment.

During the dose escalation phase I part, at each new dose level, the IMPs will be firstly administered to one patient. If no medically important or life-threatening toxicity occurs during a 1 week observation period, the subsequent patients will be allowed to start treatment without further delays between subsequent patients. The dose increase between two dose levels will be guided by the observed toxicities.

A specific monitoring of potential cardiac, haematological, liver, etc. toxicities will be set up as described in [section 8](#).

4.1.3.2. Dose administration schedules

The initial schedule will consist of a 2-week S64315 lead-in dose period followed by a 28-day cycle with the combination, i.e. a weekly regimen for S64315 and a daily regimen for azacitidine over 7 days.

Alternative dosing schedules based on the observed clinical safety, PK/PD data and non-clinical data (in vitro, in vivo, PK/PD modelling data) may be further explored. They should be integrated in the protocol via an amendment.

S64315 will be administered via intravenous (IV) infusion over at least 2h once every week, as follows:

- **2-week lead-in dose period** i.e. fixed lead-in dose 1 (LID1) of 25 mg on D-13 and fixed lead-in dose 2 (LID2) of 50 mg on D-6
- followed by the **combination treatment period over 28-day cycles**, i.e. on CxD2, CxD9, CxD16 and CxD23

The starting dose will be 50 mg. A panel of dose from 25 mg (-1) and up to 250 mg could be explored according to the dose escalation process of the BLRM. For more details, please refer to [Table \(4.1.3.3\) 1](#).

A minimum of 5 days between two infusions of S64315 is required.

An infusion could be postponed in case of 1-day delay and should be discussed with the Sponsor in case of 2-day delay, for any reason other than medical / toxicity.

Azacitidine will be administered during the combination treatment period at 75 mg/m² via subcutaneous (SC) injection, daily for 7 days, i.e. from CxD1 to CxD7, followed by a rest period of 21 days (28-day cycle).

On days of concomitant administration of S64315 and azacitidine (CxD2), azacitidine should be administered 2h (\pm 10 min) prior to S64315.

4.1.3.3. Dose escalation scheme

An adaptive Bayesian Logistic Regression Model (BLRM) with overdose control (EWOC) will be used to guide the dose escalation of S64315 in combination with azacitidine. The dose escalation will only concern S64315.

All available data on DLTs (assessed from the LID period and up to the end of cycle 1) will be used for updating the model. Before making a decision regarding dose escalation, the minimum number of patients required from a cohort must have been treated with one cycle of the combination and be fully evaluable for treatment-related toxicities according to the minimum requirements for inclusion in the Dose-Limiting Toxicity Evaluable Set (DLTES) (see [section 4.1.3.5](#)). If a patient is not eligible for inclusion in the DLTES, this patient must be replaced.

The dose allocation methodology is detailed in [section 10](#).

A maximum of 6 DLT-evaluable patients may be initially enrolled at a new dose level, and a minimum of 3 DLT-evaluable patients must be treated at a given dose level in order to begin treatment of patients at a new, higher dose level. To better characterize the safety, tolerability, PK, PD, or preliminary clinical activity of S64315 in combination with azacitidine, more than 6 DLT-evaluable patients may be treated in a cohort. If the starting dose of the combination is not well tolerated, a dose level-1 will be considered. Intermediate doses may be tested, if needed. For more details, please refer to Table (4.1.3.3) 1. A minimum of 6 DLT evaluable patients must have been evaluated at the dose considered to be the MTD, and before treating patients with this dose in the Phase II part of the study.

Table (4.1.3.3) 1 - Provisional dose levels of S64315

Dose level	Proposed dose*	Increment from previous dose
-1**	25 mg	-50%
1	50 mg	Starting dose
2	100 mg	100%
3	200 mg	100%
4	250 mg	25%

*It is possible for additional and/or intermediate dose levels to be added during the course of the study. Cohorts can be added at any dose level below or at the MTD in order to better understand safety, PK or PD

**No dose reduction below dose level -1 is permitted for this study

4.1.3.4. Intra-patient dose escalation

Intra-patient dose escalation of S64315 is not permitted at any time within the first 4 cycles of treatment. After Cycle 4 is completed, individual patients may be considered for treatment at a dose of S64315 higher than the dose initially assigned. For a patient to be treated at a higher dose of S64315, he/she must have tolerated its originally assigned dose for at least the last 4 cycles of therapy prior to the intra-patient dose escalation (i.e. he/she must not have experienced any S64315-related or S64315/azacitidine-related toxicity CTCAE Grade ≥ 2 at the originally assigned dose). Moreover, the newly assigned higher dose with which the patient is to be treated must have been validated, i.e. it should be a dose lower than the dose of the combination currently tested and considered safe according to the EWOC criterion at the time of the decision to escalate the dose of the patient. S64315 dose increase can occur as often as deemed necessary. For any further increase after the initial intra-patient dose escalation, the same rules should be applied.

Consultation and agreement with the Sponsor must occur prior to any intra-patient dose escalation. Data from the first cycle of treatment at the new dose levels will not be formally included into the statistical model describing the relationship between doses combined and occurrence of DLT. However, this data will be incorporated into the clinical assessment of safety within a dose escalation EoC meeting.

4.1.3.5. DLT definition

A dose-limiting toxicity (DLT) is defined as a clinically significant adverse event graded according to the National Cancer Institute Common Terminology Criteria for Adverse Events (NCI CTCAE) v5.0, observed following the administration of the test drug, assessed as unrelated to disease progression, intercurrent illness, or concomitant medications, considered at least possibly related to the test drug by the investigator and that meets any of the criteria included in Table (4.1.3.5) 1.

For each patient, an assessment of DLT will be performed at the end of the first cycle of treatment, through C1D28. This assessment will include all toxicities observed starting from the LID period through C1D28. Only DLTs occurring during the LID period + Cycle 1 will be included in the Bayesian logistic regression model (BLRM) that estimates the relationship between dose and DLTs. However, monitoring for DLTs that occur after Cycle 1 will continue, in case there is evidence for delayed or cumulative toxicity.

Table (4.1.3.5) 1 - Toxicity criteria according to NCI CTCAE grading

TOXICITY	DLT CRITERIA
Eye disorders: blurred vision; cataract; corneal ulcer; dry eye; eye pain	Grade ≥ 3 confirmed by an ophthalmologic examination
GI disorders	Grade ≥ 3 nausea, vomiting or diarrhoea resulting in hospitalization, tube-feeding or use of total parenteral nutrition (TPN) Grade 4 diarrhoea
Renal abnormalities	Grade ≥ 3 serum creatinine
Hepatic abnormalities	AST or ALT ≥ 3 xULN along with a total bilirubin > 2.0 xULN and confirmed Hy's law cases according to FDA guidance; For patients with elevated baseline AST or ALT or total bilirubin: [AST or ALT > 2.0 xbaseline AND > 3.0 xULN] OR [AST or ALT > 8.0 xULN], whichever is lower, combined with [total bilirubin > 2.0 x baseline AND > 2.0 xULN] Isolated Grade 3 AST or ALT which does not resolve within 7 days to Grade ≤ 1 Isolated Grade 4 AST or ALT
For any Grade ≥ 3 hepatic toxicity which does not resolve within 7 days to Grade ≤ 1 level or baseline, an abdominal CT scan or hepatic echography must be performed.	
Pancreatic abnormalities	Grade ≥ 3 serum lipase and/or serum amylase Grade ≥ 3 pancreatitis
For any Grade 3 or Grade 4 pancreatic toxicity, which does not resolve within 7 days to Grade ≤ 1 level or baseline, an abdominal CT scan must be performed	
Creatine kinase (CK) / Creatine phosphokinase (CPK)	Grade ≥ 3 serum CK/CPK Grade 3 isolated electrolyte abnormalities (i.e. those occurring without clinical consequence) not recovered with or without intervention, to Grade < 2 level within 72 hours

TOXICITY	DLT CRITERIA
Electrolyte abnormalities (including magnesium, calcium, phosphorus, etc.) clinically significant	Any Grade 4 electrolyte abnormality
Cardiac disorders	QTcF interval \geq 501 ms or increase of $>$ 60 ms from baseline on at least two separate ECG assessments (1 assessment = triplicate ECG) Asymptomatic, absolute decrease in LVEF of 10% or greater from baseline AND LVEF $<$ 50% Asymptomatic, absolute decrease in LVEF of 20% or greater from baseline Troponin increase $>$ 10xULN or a troponin increase consistent with the diagnosis of a myocardial infarction (Grade 3) Symptomatic congestive heart failure
Skin and subcutaneous tissue disorders	Grade \geq 3 rash
Haematological abnormalities	Grade 4 neutropenia and/or thrombocytopenia persisting for 28 days after the start of azacitidine dosing in a cycle of therapy in the absence of active AML ($<$ 5% blasts) or active MDS or myelofibrosis
Other AEs	Any Grade \geq 3 AE Single event or multiple occurrences of the same event that lead to a dosing delay of $>$ 7 days in a cycle may be considered to be DLT by the Investigators and the Sponsor, even if not Grade \geq 3 Failure to restart test drug administration at the same dose due to drug-related toxicity Failure to restart test drug administration at the same dose within one cycle (i.e. 28 days) of the first missed dose due to delayed recovery from drug-related toxicity Failure to initiate cycle 1 after completing the LID period or failure to receive LID2 after receiving the LID1, due to drug-related toxicity
NCI CTCAE v5.0 will be used for grading	

The following criteria will not be considered as DLT:

- Grade 3 nausea, vomiting, diarrhoea, anorexia or constipation that do not result in hospitalization, tube-feeding or use of TPN
- Grade 3 fatigue, asthenia, fever
- Grade 3 isolated electrolyte abnormalities (i.e. those occurring without clinical consequence) that resolve, with or without intervention, to Grade $<$ 2 level in 72 hours

Patients who meet any of the criteria included in Table (4.1.3.5) 2 at the end of Cycle 1 will not be evaluable for DLT and therefore will be replaced during the dose escalation phase I part of the study, but not in the expansion parts of the study.

Table (4.1.3.5) 2 - Non evaluability criteria

Permanently discontinued treatment before C1D28 for reasons other than DLT
Did not undergo a DLT assessment at the end of Cycle 1
Did not receive the minimum exposure criteria i.e. minimum number of doses according to the dose administration schedule of both IMPs prescribed from study entry to DLTs assessment visit (end of Cycle 1 D28), unless treatment was stopped for a DLT - see Table (4.1.3.5) 3
If a patient received more than the assigned IMP doses from study entry to DLT occurrence during the DLT assessment period, non-evaluability criteria will be reassessed by Sponsor and investigator - see Table (4.1.3.5) 3

Table (4.1.3.5) 3 - Minimum number of S64315 and azacitidine doses to meet minimum exposure until the end of cycle 1

Schedule description	Minimum number of doses
S64315 during the 2-week LID period (LID1 on D-13 and LID2 on D-6)	2 out of 2
S64315 (D2, D9, D16 and D23 in 28-day cycle)	3 out of 4
Azacitidine (D1 to D7 in 28-day cycle)	5 out of 7

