MedDRA	: Medical Dictionary for Regulatory Activities
mg	: Milligram
MI	: Myocardial Infarction
min	: Minute
mL	: Millilitre
mm	: Millimetre
mmHg	: Millimetre of mercury
mmol	: Millimole
msec	: Millisecond

MLFS	: Morphologic Leukaemia-Free State
MM	: Multiple Myeloma
MRD	: Minimal (measurable) Residual Disease
MS/MS	: tandem Mass Spectrometry
MTD	: Maximum Tolerated Dose
MUGA scan	: Multi-Gated Acquisition scan
NA	: Not Applicable
NAE	: Number of Adverse Events
NCA	: Non-Compartmental Analysis
NCI	: National Cancer Institute
NCT	: EudraCT Number
NGS	: Next Generation Sequencing
ng	: Nanogram
NTI	: Narrow Therapeutic Index
NS	: Not statistically Significant
NYHA	: New York Heart Association
OPM	: OPERating Manual
ORR	: Overall Response Rate
OS	: Overall Survival
p.o.	: per os (orally)
PBMC	: Peripheral Blood-derived Mononuclear Cells
PBPK	: Physiologically-based Pharmacokinetic
PD	: Pharmacodynamics
PDX	: Patient-Derived Xenograft
PFS	: Progression Free Survival
PG	: Pharmacogenomics
P-GP	: P-glycoprotein 1
Ph. Eur.	: European Pharmacopeia
PK	: Pharmacokinetics
PR	: Partial response
po	: per os (orally)
PPS	: Per Protocol Set
PS	: Performance Status
QC	: Quality Control
QD	: Once daily
QTc	: QT interval corrected for heart rate
QTcF	: QTc interval corrected with Fridericia's formula
RBC	: Red Blood Cells
RNA	: Ribonucleic acid
RP2D	: Recommended Phase II Dose
SAE	: Serious Adverse Event
SBP	: Systolic Blood Pressure
SC	: SubCutaneous (route)
SD	: Standard Deviation
SLL	: Small Lymphocytic Lymphoma
SE	: Standard Error
sec	: Second
SmPC	: Summary of Product Characteristics
SoI	: Start of Infusion
SS	: Safety Set

SUSAR	: Suspected Unexpected Serious Adverse Reaction
T	: Temperature
$t_{1/2}$: terminal half-life
TdP	: Torsades de Pointes
test drug	: Drug substance in a given dosage form, tested in a clinical trial, i.e. S64315
t_{last}	: Time corresponding to C_{last}
TLS	: Tumour Lysis Syndrome
t_{max}	: Time corresponding to C_{max}
TPN	: Total parenteral nutrition
TSH	: Thyroid Stimulating Hormone
TTE	: TransThoracic Echocardiography
TU	: Therapeutic Unit
ULN	: Upper Limit of reference range
USP-NF	: United States Pharmacopeia and The National Formulary
Vd	: Volume of distribution
WBC	: White Blood Cells
WHO	: World Health Organization
WHO-DD	: World Health Organization, Drug Dictionary
WMA	: World Medical Association
WOCBP	: Woman of Child Bearing Potential
WV	: Withdrawal Visit

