4.3. Study products and blinding systems

4.3.1. Products administered

Arm A

S64315 (test drug) and azacitidine administered in combination are both IMPs in Arm A.

Azacitidine will be provided as marketed boxes.

Les Laboratoires Servier Industrie (Gidy, France) will:

- pack, release and supply S64315 Therapeutic Units (TUs);
- relabel, release and supply azacitidine marketed boxes.

Table (4.3.1) 1 provides a description of the IMPs.

Table (4.3.1) 1 - Description of the IMPs (S64315 and azacitidine)

	S64315 Organic concentrate	S64315 Liposomal vehicle	Azacitidine
Pharmaceutical form	Concentrate of solution for infusion	Intravenous infusion	Powder for suspension for injection
Unit dosage	209.95 mg/3.4mL	2.39 gram of egg phospholipids in 23.9 mL	100 mg
Appearance, colour	Colourless to greenish, yellowish or slightly brownish, clear solution	A yellow to brown turbid solution	White lyophilized powder
Composition	Each vial contains an overfill volume of 0.4 mL, so it actually contains 234.65 mg of S64315. The vials contain a clear, colourless to greenish, yellowish or slightly brownish solution comprising of the active ingredient S64315, propylene glycol, anhydrous ethanol, DMPG (1,2-Dimyristoyl-sn-1-glycero)-3-phospho-rac-glycerol sodium salt), PEG 300 (Polyethylene glycol 300)	Each vial contains 2.39 gram of egg phospholipids. The liposomal vehicle comprises egg phospholipids, sucrose, L-histidine and water for injections. Sodium hydroxide for injections and hydrochloric acid are also used for pH adjustment. The egg phospholipids comprising liposomal vehicle form small liposomes in aqueous environment and are used as a solubilizing vehicle, able to dissolve S64315 in an aqueous environment after mixing with S64315 liquid in the vial	Each vial contains 100 mg azacitidine. After reconstitution, each mL of suspension contains 25 mg azacitidine. Excipient: <

Table (4.3.1) 2 provides a description of the packaging of the IMPs.

Table (4.3.1) 2 - Description of packaging

Number of units of the pharmaceutical form per primary packaging	- 3.8 mL of S64315 concentrate for solution for infusion in individual 6 mL glass vial - 23.9 mL of liposomal vehicle in individual 30 mL glass vial - 100 mg of azacitidine powder for suspension for injection in individual vial
Number of primary packaging per secondary packaging	1 vial of S64315 concentrate per box 1 vial of S64315 liposomal vehicle per box 1 vial of azacitidine per box

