10.2.2. Statistical model

This part contains a quick presentation of the model; more details about the model and assumptions are presented in [Appendix 8](#), as well as the operational characteristics of the chosen models.

A 5-parameter adaptive Bayesian logistic regression model guided by the escalation with overdose control principle (EWOC) will be fitted on DLT during LID period and during Cycle 1 data to make dose recommendations and estimate the MTD/ RP2D for the combination of S64315 (agent 1) and azacitidine (agent 2, fixed dose).

The model has three components:

- S64315 single agent toxicity, represented by parameters α_1 and β_1
- azacitidine single agent toxicity, represented by parameters α_2 and β_2
- the interaction between S64315 and azacitidine, represented by parameter η_{12}

The two single agent dose-DLT relationships are modelled as in a single agent study:

$$\begin{aligned} \text{logit}(\pi_1(d_1)) &= \log(\alpha_1) + \beta_1 \log(d_1/d_1^*), \alpha_1 > 0, \beta_1 > 0 \\ \text{logit}(\pi_2(d_2)) &= \log(\alpha_2) + \beta_2 \log(d_2/d_2^*), \alpha_2 > 0, \beta_2 > 0 \end{aligned}$$

where $\pi_1(d_1)$ is the probability of DLT if S64315 is given as a single agent at a total weekly dose of d_1 and $\pi_2(d_2)$ is the probability of DLT if azacitidine is given as a single agent at a total daily dose of d_2 .

The parameter α_1 (respectively α_2) is then the single-agent odds of a DLT at the reference dose for S64315 (respectively azacitidine), and β_1 (respectively β_2) is the increase in the log-odds of a DLT by a unit increase in log-dose for S64315 (respectively azacitidine). As there is only one tested dose of azacitidine and this tested dose is chosen as the reference dose, $\log(d_2/d_2^*) = 0$ and β_2 will not be estimated. Then, the model is simplified from a 5-parameter model to a 4-parameter model.

The dose-DLT relationship of the combination of S64315 and azacitidine is modelled as:

$$\begin{aligned} \text{Odds}(\pi_{12}(d_1, d_2)) &= \frac{\pi_{12}(d_1, d_2)}{1 - \pi_{12}(d_1, d_2)} \\ &= \exp(\eta_{12} \frac{d_1}{d_1^*} \frac{d_2}{d_2^*}) \left(\frac{\pi_1(d_1) + \pi_2(d_2) - \pi_1(d_1)\pi_2(d_2)}{(1 - \pi_1(d_1))(1 - \pi_2(d_2))} \right) \end{aligned}$$

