This study is currently planned to administer S64315 once weekly with a 28-day cycle preceded by a LID period of 2-weeks, with one infusion of 25 mg on D-13 and one infusion of 50 mg on D-6. Azacitidine will be administered at 75 mg/m² via SC injection, daily for 7 days, from D1 to D7 followed by a rest period of 21 days (28-day cycle). However, based on the emerging clinical safety and PK data, other dosing schedules may also be assessed in this study.

If the decision is made to switch to a different dosing schedule before determination of the MTD in the planned schedule, then the initial total weekly S64315 dose will be a dose that has previously been tested and that is considered safe according to the EWOC criterion. Unless otherwise justified, it will be assumed that different schedules can have different effects on patient safety and dose allocation based on the new schedule will then be guided by a new model.

The new model and its operating characteristics would be communicated via a new document similar to [Appendix 8](#) along with the documentation provided as formal notification of the change in dosing schedule (e.g. minutes of the corresponding dose escalation meeting, etc.), or it would be explicitly indicated in such documentation with suitable rationale that the new regimen has no change to the initial model.

The MTD is the highest dose of the combination treatment that is unlikely (< 25% posterior probability) to cause DLT in more than 33% of the treated patients during the LID period and the first cycle of S64315 treatment in combination with azacitidine.

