1.1.2. Prior for azacitidine

The normal prior for the BLRM parameters (α_2, β_2) of the dose-DLT relationship of azacitidine is defined as a weakly-informative prior. The information available on azacitidine (e.g. SmPC) have been used to define the prior parameter alpha. As there is only one dose for azacitidine, and as the reference dose is equal to this only dose, there is no estimation of β_2 , then there is now only one parameter estimated for this agent. However, a prior has been defined anyway on β_2 to keep the opportunity to add another dose of azacitidine, if the matter appears in the future.

With a reference dose level of 75 mg/m², the prior parameters are obtained as follows:

- The median DLT rate at the azacitidine reference dose (75 mg/m²) was fixed such that the mean DLT rate at this dose, with the considered standard deviation, was equal to 8%, leading to a median DLT rate of 2.3, i.e. $\text{mean}(\log(\alpha_2)) = \log(0.023/0.977)$ (see prior distribution in Table (1.1.2) 2)
- A doubling in dose was assumed to double odds of DLT, i.e. $\text{mean}(\log(\beta_2)) = 0$
- The standard deviation of $\log(\alpha_2)$ was set to 2 which allows for strong prior uncertainty for the dose-toxicity profile of azacitidine
- The correlation between $\log(\alpha_2)$ and $\log(\beta_2)$ was set to 0

Table (1.1.2) 1 summarizes these prior parameters.

Table (1.1.2) 1 - Prior parameters for bivariate normal distribution of model parameters (α_2, β_2) for azacitidine

Parameters	Means	Standard deviations	Correlation
$\log(\alpha_2), \log(\beta_2)$	(-3.75, 0)	(2, 1)	0

Resulting distribution and associated summary statistics are presented in Table (1.1.2) 2.

Table (1.1.2) 2 - Prior distribution summaries for azacitidine derived from priors in Table (1.1.1.2) 1

Azacitidine dose (mg/m ²)	Prior probabilities that Pr(DLT) is in interval:			Mean	SD	Quantiles			ESS ¹
	[0, 0.16)	[0.16, 0.33)	[0.33, 1]			2.5%	50%	97.5%	
75	0.8574	0.0795	0.0631	0.0803	0.1404	5,00E-04	0.0230	0.5417	2.7493

¹: Effective sample size

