4.2.3. Safety**4.2.3.1. Dose Limiting Toxicity (DLT)**

A DLT is defined as:

- A clinically significant adverse event graded according to the NCI-CTCAE version 5.0, observed following the administration of the test drugs.
- Assessed as unrelated to disease progression, intercurrent illness, or concomitant Medications.
- At least possibly related to the test drug(s) by the investigator and meeting any of the criteria included in [Table \(4.2.3.1\) 1](#).

DLT will be reported based on investigator, using the ‘Dose limiting toxicity (DLT)’ / ‘Adverse event’ e-CRF page, and not recalculated.

Table (4.2.3.1) 1 –Toxicity criteria

TOXICITY	DLT CRITERIA
Eye disorders: blurred vision; cataract; corneal ulcer; dry eye; eye pain	Grade ≥ 3 confirmed by an ophthalmologic examination
GI disorders	Grade ≥ 3 nausea, vomiting or diarrhoea resulting in hospitalization, tube-feeding or use of total parenteral nutrition (TPN) Grade 4 diarrhoea
Renal abnormalities	Grade ≥ 3 serum creatinine
Hepatic abnormalities	AST or ALT ≥ 3 xULN along with a total bilirubin > 2.0 xULN and confirmed Hy’s law cases according to FDA guidance; For patients with elevated baseline AST or ALT or total bilirubin: [AST or ALT > 2.0 xbaseline AND > 3.0 xULN] OR [AST or ALT > 8.0 xULN], whichever is lower, combined with [total bilirubin > 2.0 x baseline AND > 2.0 xULN] Isolated Grade 3 AST or ALT which does not resolve within 7 days to Grade ≤ 1 Isolated Grade 4 AST or ALT
For any Grade ≥ 3 hepatic toxicity which does not resolve within 7 days to Grade ≤ 1 level or baseline, an abdominal CT scan or hepatic echography must be performed.	
Pancreatic abnormalities	Grade ≥ 3 serum lipase and/or serum amylase Grade ≥ 3 pancreatitis
For any Grade 3 or Grade 4 pancreatic toxicity, which does not resolve within 7 days to Grade ≤ 1 level or baseline, an abdominal CT scan must be performed	
Creatine kinase (CK) / Creatine phosphokinase (CPK)	Grade ≥ 3 serum CK/CPK Grade 3 isolated electrolyte abnormalities (i.e. those occurring without clinical consequence) not recovered with or without intervention, to Grade < 2 level within 72 hours

Electrolyte abnormalities (including magnesium, calcium, phosphorus, etc.) clinically significant	Any Grade 4 electrolyte abnormality

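### The protocol ties a DLT to S64315 alone, while the MTD, the dose-toxicity model and the SAP wording refer to the combination, so the primary endpoint is defined two ways

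*Protocol*

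**What the plan says.** Protocol 4.1.3.5 requires a DLT to follow administration of the test drug and to be "considered at least possibly related to the test drug by the investigator". This sentence governs every row of Table (4.1.3.5) 1. The list of abbreviations defines test drug as "Drug substance in a given dosage form, tested in a clinical trial, i.e. S64315". Section 4.3.1 keeps the same distinction: "S64315 (test drug) and azacitidine administered in combination are both IMPs in Arm A".

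The quantity being estimated is about both drugs. Section 10.2.2 states "The MTD is the highest dose of the combination treatment that is unlikely (< 25% posterior probability) to cause DLT" in more than 33% of treated patients, over the lead-in and first combination cycle. The model in that section has a component for "azacitidine single agent toxicity, represented by parameters" of its own, alongside the S64315 and interaction components. In Appendix 8, section 1.1.2, the azacitidine prior is set so that the mean DLT rate at 75 mg/m² "was equal to 8%, leading to a median DLT rate of 2.3" (in percent).

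SAP 4.2.3.1 speaks of test drugs in the plural and requires the event to be "At least possibly related to the test drug(s) by the investigator". It then says DLTs are taken from the investigator's entries and not re-derived. SAP 3.4.1 tabulates and lists DLTs in the DLT-evaluable set only.

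**The concern.** The model's likelihood is for the DLT probability of the combination, and the 33% limit applies to that probability. If the events fed into it must be attributable to S64315, a toxicity caused by azacitidine alone belongs to the modelled rate but not to the data. The observed rate is then too low for the stated target, which is the unsafe direction for escalation.

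The SAP does not close the gap. Its wider wording cannot recover events that sites did not declare under the narrower protocol wording, so the report could describe one endpoint while presenting another. The incidence of DLTs is among the primary endpoints.

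Such events are plausible on the protocol's own account. Section 2.3.3 names myelosuppression as the main dose-limiting toxicity of azacitidine and lists injection site reactions among its common effects. Azacitidine is given subcutaneously and S64315 intravenously, so a severe injection-site reaction is one case where S64315 could be excluded.

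**Working it through.** **Where an azacitidine-only cycle 1 toxicity goes.** The lead-in uses S64315 alone, so the question arises only in cycle 1. Two routes follow from 4.1.3.5 and Table (4.1.3.5) 2:

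- The patient continues with the minimum exposure to both drugs. The patient stays evaluable and counts as having no DLT.
- The patient stops permanently before day 28 of cycle 1, or misses the minimum exposure. The reason is not a DLT, so the patient is non-evaluable and is replaced.

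Take five patients, one with an S64315-related DLT and one with an azacitidine-only event. Counting both gives 2/5 = 40%. The first route gives 1/5 = 20%. The second gives 1/4 = 25%, or 1/5 = 20% if the replacement has no DLT.

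**Reproducing the plan's figures.** Inputs from Appendix 8:

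- S64315 power prior: means (−0.092, −0.507), SDs (0.982, 0.694), correlation 0.705, reference dose 1400 mg.
- Azacitidine: log-odds with mean log(0.023/0.977) and SD 2.
- Interaction: mean 0, SD 9.902, which equals log(2)/1.96 × 1400/50.

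The combination odds are exp(η·d/1400) × [p1 + p2 − p1·p2]/[(1 − p1)(1 − p2)]. Two million draws gave:

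| Quantity | Printed | Reproduced |
|---|---|---|
| Azacitidine mean / median | 0.0803 / 0.0230 | 0.080 / 0.023 |
| S64315 alone, 50 mg, mean | 0.108 | 0.108 |
| Combination, 50 mg, mean | 0.184 | 0.183 |
| Combination, 50 mg, P(rate ≥ 33%) | 0.143 | 0.144 |
| After 1/5 at 50 mg, P(rate ≥ 33%) at 100 mg | 0.2246 | 0.222 |
| After 2/5 at 50 mg, P(rate ≥ 33%) at 25 mg | 0.2032 | 0.194 |

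**Size of the azacitidine contribution at 50 mg.** These figures suppose that every azacitidine toxicity is attributed to azacitidine alone and goes uncounted:

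- Means: 18.4% − 10.8% = 7.6 points.
- Means without interaction: 0.108 + 0.0803 − 0.108 × 0.0803 = 0.180, and 18.0% − 10.8% = 7.2 points.
- Medians: 14.0% − 8.8% = 5.2 points.
- With the azacitidine term removed and the interaction kept, the mean falls from 0.183 to 0.111 and P(rate ≥ 33%) from 0.144 to 0.038.

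**What one event can do.** In Table (1.3) 1, 1/5 at 50 mg leads to 100 mg and 2/5 leads to 25 mg. If one of two DLTs is azacitidine-only and uncounted, the model sees 1/5 instead of 2/5.

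**How often, under an assumption.** The documents give no rate of azacitidine-only DLTs. If it were as high as the azacitidine prior median or mean, the chance of at least one in five patients would be 1 − 0.977⁵ = 11% or 1 − 0.92⁵ = 34%. These too are ceilings.

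**The case against.** The strongest reply is that few events can be lost. Protocol 4.1.3.5 asks only for a possible relation, and 8.8 treats an event as related unless the relationship can be excluded. Every patient has received S64315 twice before the first azacitidine dose and weekly afterwards, and 2.3.4 expects overlapping marrow and gastrointestinal toxicity. To lose an event, the investigator must rule S64315 out. This stands and limits the size.

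The protocol's terms may also simply be loose. Section 4.1.3.3 speaks of treatment-related toxicity, some DLT rows say only drug-related, and the haematological row is timed from the start of azacitidine. That is possible, but 4.1.3.4 does separate toxicity related to S64315 from toxicity related to both drugs, and no passage makes a relation to azacitidine alone sufficient for a DLT. The DLT form is not in the documents, so what sites applied is unknown.

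Other safeguards exist. The model is guidance only, end-of-cohort meetings and the DSMB review all safety data, and SAP 3.4.2 reports adverse events by relationship. None of these shows the DLT rate under the other definition.

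A reader might infer that every azacitidine-only toxicity is scored as no DLT. The documents do not support this: those that end treatment or break minimum exposure remove the patient from the evaluable set. A reader might also take the 8% azacitidine prior mean as the size of the bias. It is the mean of a deliberately vague prior (effective sample size 2.7, median 2.3%) for all azacitidine DLTs, not only those where S64315 is excluded. The 1/5 against 2/5 example shows the leverage of one event in a small cohort, which any DLT rule shares.

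**Conclusion.** The mismatch is real. Read literally, the protocol's DLT definition is narrower than the rate that its MTD and model refer to, and the SAP states a third, wider wording that it does not apply to the data. Both routes for an azacitidine-only toxicity can lower the observed combination DLT rate.

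The size is unknown. About 5 to 8 points at 50 mg is a ceiling that rests on the protocol's priors and on every azacitidine toxicity being attributed to azacitidine alone; the relatedness test makes the likely effect smaller.

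A reader might infer that escalation was in fact pushed too far. Nothing in the documents shows that any such event occurred. SAP 1.3 and 1.3.1 record that escalation was stopped and expansion will not be conducted. What remains is the definition and reporting of a primary endpoint.

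**What to change.** Reconcile Protocol 4.1.3.5, the test-drug definition (abbreviations and 4.3.1), the MTD definition in 10.2.2 and SAP 4.2.3.1, so that protocol and SAP state the same causality requirement. Because 4.1.3.6 makes a DLT trigger a treatment delay, which requirement applies is for the sponsor and investigators to settle, not this review. The report should state which wording sites worked to.

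In SAP 3.4.1, add a listing on the Safety Set of cycle 1 adverse events that meet a Table (4.1.3.5) 1 criterion but were attributed to azacitidine only. Include patients left out of the DLT-evaluable set because of them. Show the DLT rate by dose level with and without these events as a sensitivity analysis.

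Attribution to each drug is already collected (SAP 4.2.3.2), so the cost is one extra output. Some medical review is needed, because clinical significance and exclusion of disease progression are judgements. The DLT rate in the sensitivity analysis may be slightly higher.
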